5.3 Pretreatment Period

Pretransplant Evaluations

The following observations must be completed within 30 days before the initiation of the conditioning regimen.

- History, physical examination, height, and weight.
- CBC with differential will be performed as appropriate during hospitalization for alloHCT on clinic visits and at minimum performed on days indicated on the schedule of events.
- Comprehensive metabolic panel will be performed as appropriate during hospitalization for alloHCT, on clinic visits and at minimum performed on days indicated on the schedule of events.
- HLA typing (donor and recipient).
- Adverse events assessments.
- Karnofsky Performance Status Scale and HCT-Specific Comorbidity Index score.
- Infectious disease markers: CMV antibody, hepatitis panel (HepA Ab, HepB SAb, HepB SAg, HepB Core Ab, HepC Ab), HIV and HTLV I/II antibody.
- EKG and LVEF (may be performed <30 days prior to patient enrollment).
- Pulmonary function tests, including DLCO and FEV1 (may be performed <30 days prior to patient enrollment).
- Disease evaluation of the malignant disease: For acute leukemia, CML and MDS, this includes a bone marrow aspirate and biopsy for pathology and cytogenetics.

- Pregnancy test per institutional practices for females of childbearing potential.
 NOTE: pregnancy test must be performed <30 days before initiation of the conditioning regimen.
- Pretransplant blood samples for future research.

Research (stool) sample will be collected pretransplant after admission to the hospital during the (pretransplant) conditioning period. Samples will be collected from each patient as a baseline and then at weekly intervals through the period of engraftment. In addition, stool samples will be obtained at the time of GVHD onset in any affected patients. Fresh fecal samples will be collected and immediately preserved in RNAlater solution, to facilitate optimal sample preservation, consistency of sample quality and ease of sample transport. Genomic DNA will be isolated from 200 mg of fecal sample using the Qiagen Powerlyzer Powersoil kit as described. Bacterial composition and abundance will be validated by quantitative PCR analysis. Composition of the microbiota will be determined through sequencing of the 16S rRNA gene V4 region (Diversigen, Baylor College of Medicine, Waco, TX). PCR products will be generated using a dual-indexing amplification strategy, then sequenced on the MiSeq platform (Illumina, San Diego, CA).

5.4 Study Procedures during Treatment

Patients must meet eligibility criteria eligible on day -1 to be treated.

5.5 GVHD Assessment

Patients will be monitored for development of acute and chronic GVHD, per standard operating procedures at the MCW BMT Program, but at minimum on days +28 (+/-7), +56 (+/-7), +100 (+/-14), +180 (+14), +365 (+/-28) post-HCT. Diagnosis of acute GVHD may not necessitate biopsy confirmation in at least one involved organ but would be preferred. When more than one organ is involved, biopsy confirmation of all involved organs is recommended but not necessary. With liver-only GVHD, biopsy confirmation is strongly recommended. Acute GVHD will be assessed by consensus criteria (Appendix 2), and chronic GVHD diagnosis and grading will be according to NIH Criteria (please see Appendix 2).

Independent GVHD adjudication is mandated in the study. Acute and chronic GVHD will be adjudicated by an independent Faculty Research Committee (FRC)-appointed review panel. Protocol PIs will be blinded to the adjudication panel and will not be permitted to grade or modify GVHD assessments. GVHD case report forms (CRFs) will be completed by treating MDs/NPs/APPs in real time, as indicated in study calendar. FRC adjudication panel will grade GVHD, using a calendar-driven approach (days +100 and +180 for aGVHD and days +180 and +365 for chronic GvHD).

6 TREATMENT PLAN

6.1 Investigational Agent Administration

Treatment will be administered on an inpatient or outpatient basis depending on patient status. Treatment cannot be self-administered. Allow prefilled syringe in original carton to sit and reach room temperature (30 minutes) before injecting subcutaneously. Inject a site with clear skin and easy access (e.g., abdomen, thighs, or upper arm); do not administer two inches around navel or where skin is tender, bruised, erythematous, indurated, or affected by psoriasis; do not inject into scars, stretch marks, or blood vessels.

Study Drug	Premedication; precautions	Dose	Route	Schedule (Day pre or post- transplant)
Tildrakizumab	None	100 mg	Subcutaneously	Day -1, Day 28 ± 3, Day 112 ± 7, Day 196 ± 14, and Day 280 ± 14.

The following are contraindications for tildrakizumab dosing beyond the first dose:

- 1) Grade 4 (according to CTCAE version 5 hematologic or nonhematologic events (which have life-threatening consequences and require urgent treatment). Dosing will be allowed upon recovery to grade ≤3. Transfusion to increase platelet and hemoglobin is allowed.
- 2) Disease (relapse or progression of the primary malignancy) for which treatment is indicated.
- 3) Donor leukocyte infusion (DLI) prior to planned redose of tildrakizumab for any indication: infection, disease control or to address mixed chimerism.
- 4) Grade III–IV acute GVHD. Patients with grade I–II acute GVHD and on topical or systemic corticosteroids therapy (equivalent to prednisone ≤20 mg/d) can receive a second dose of tildrakizumab.
- 5) Active chronic GVHD requiring systemic therapy.

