4.6 Discontinuation of Study Treatment, Withdrawal, and Compliance

Discontinuation from the study treatment does not mean discontinuation from the study. Subject will be considered in follow-up, study procedures should still be completed as indicated by the study protocol and AEs/SAEs will continue to be reported according to this protocol.

In the absence of treatment delays due to adverse events, study treatment/intervention may continue until:

- Disease (relapse or progression of the primary malignancy) for which treatment is indicated.
- Donor leukocyte infusion (DLI) prior to planned redose of tildrakizumab for any indication: infection, disease control or to address mixed chimerism.
- Grade III-IV acute GVHD. Patients with grade I-II acute GVHD and on topical or systemic corticosteroids therapy (equivalent to prednisone ≤20 mg/d) can receive further doses of tildrakizumab.
- Active chronic GVHD requiring systemic therapy.
- General or specific changes in the subject's condition renders the subject unacceptable for further treatment in the investigator's judgment.
- Inter-current illness that prevents further treatment administration.
- Subject decides to withdraw from the study.
- The subject has significant noncompliance with the protocol (see below).
- Unacceptable adverse event(s) beyond requirements as detailed in this protocol.

Subjects who sign the informed consent form, and are enrolled and receive the study intervention. but subsequently withdraw, or are withdrawn or discontinued from the study will not be replaced.

Consent Withdrawal

A subject may decide to withdraw from the study at any time. MCWCC CTO will follow its IRB of record's SOPs regarding consent withdrawal.

If a subject intends on withdrawing consent, staff should confirm which of the following options the subject chooses and document the discussion:

- Full consent withdrawal, with no study follow-up.
- Selective consent withdrawal from interventional portion of the study, but agrees to continued follow-up of associated clinical outcome information.

Investigator-initiated Withdrawal

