7.6 Known AEs List

Tildrakizumab

Tildrakizumab side effects include:

- Nasopharyngitis
- Diarrhea
- Injection site reaction

Tacrolimus

Tacrolimus side effects include:

- Neurologic: confusion, dizziness, insomnia, seizures, tremors, changes in how clearly one can think
- Cardiovascular: hypertension
- Gastrointestinal: nausea, vomiting
- Hematologic: microangiopathic hemolytic anemia, thrombocytopenia
- Endocrine and metabolic: hypomagnesemia, hypokalemia, hyporalcemia, hyperlipidemia
- Miscellaneous: unwanted hair growth, changes in vision, liver problems, reversible renal insufficiency, infections and posttransplant lymphoproliferative disorders

Methotrexate

The most frequently reported adverse reactions associated with methotrexate use as GVHD prophylaxis include:

- Neurologic: fever, dizziness, chills, undue fatigue
- Gastrointestinal: ulcerative stomatitis, nausea, abdominal distress, diarrhea
- Hematologic: leucopenia, anemia and suppressed hematopoiesis (leading to infection)

Miscellaneous

Abnormal liver tests, kidney failure and pulmonary complications after transplantation

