APPENDIX 3. MEDICATION GUIDE

ILUMYA™ - tildrakizumab-asmn injection, solution Sun Pharmaceutical Industries, Inc.

Medication Guide

ILUMYA™ ("e-loom'-me-a") (tildrakizumab-asmn)

injection, for subcutaneous use

What is the most important information I should know about ILUMYA™?

ILUMYA™ may cause serious side effects, including:

Serious allergic reactions. Get emergency medical help right away if you get any of the following symptoms of a serious allergic reaction:

- feel faint
- swelling of your face, eyelids, lips, mouth, tongue or throat
- skin rash
- trouble breathing or throat tightness
- chest tightness

Infections. ILUMYA™ is a medicine that may lower the ability of your immune system to fight infections and may increase your risk of infections. Your healthcare provider should check you for infections and tuberculosis (TB) before starting treatment with ILUMYA™ and may treat you for TB before you begin treatment with ILUMYA™ if you have a history of TB or have active TB. Your healthcare provider should watch you closely for signs and symptoms of TB during and after treatment with ILUMYA™.

Tell your healthcare provider right away if you have an infection or have symptoms of an infection, including:

- fever, sweats, or chills
- cough
- shortness of breath
- blood in your phlegm (mucus)
- muscle aches
- warm, red or painful skin or sores on your body different from your psoriasis
- weight loss
- diarrhea or stomach pain
- burning when you urinate or urinating more often than normal

See "What are the possible side effects of ILUMYA™?" for more information about side effects.

What is ILUMYA™?

ILUMYA™ is a prescription medicine used to treat adults with moderate to severe plague psoriasis who may benefit from taking injections, pills (systemic therapy) or treatment using ultraviolet or UV light (phototherapy).

MCW Protocol No: PRO00035737 61 Version No. 7 Version Date: 10/31/2022 It is not known if ILUMYA™ is safe and effective in children under 18 years of age.

Do not use ILUMYA™ if you have had a severe allergic reaction to tildrakizumab or any of the other ingredients in ILUMYA™ . See the end of this Medication Guide for a complete list of ingredients in ILUMYA™.

Before receiving ILUMYA™, tell your healthcare provider about all of your medical conditions, including if you:

- have any of the conditions or symptoms listed in the section "What is the most important information I should know about ILUMYA™?"

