- have an infection that does not go away or that keeps coming back.
- have TB or have been in close contact with someone with TB.
- recently received or are scheduled to receive a vaccine (immunization). You should avoid receiving live vaccines during treatment with ILUMYA™.
- are pregnant or plan to become pregnant. It is not known if ILUMYA™ can harm your unborn baby.
- are breastfeeding or plan to breastfeed. It is not known if ILUMYA™ passes into your breast milk.

Tell your healthcare provider about all the medicines you take, including prescription and over-the-counter medicines, vitamins, and herbal supplements.

How will I receive ILUMYA™?

- ILUMYA[™] should only be given to you by a healthcare provider.
- ILUMYA™ is given as an injection under your skin (subcutaneous injection) in areas of your body such as your thighs, stomach area (abdomen), or upper arm.
- If you miss a follow-up appointment and do not receive your dose of ILUMYA™, schedule another appointment as soon as possible.

What are the possible side effects of ILUMYA™?

ILUMYA™ may cause serious side effects. See "What is the most important information I should know about ILUMYA™?"

The most common side effects of ILUMYA™ include:

- upper respiratory infections
- injection site reactions
- diarrhea

These are not all of the possible side effects of ILUMYA™ . Call your doctor for medical advice about side effects. You may report side effects to the FDA at [name].

General information about the safe and effective use of ILUMYA™.

Medicines are sometimes prescribed for purposes other than those listed in a Medication Guide. You can ask your healthcare provider for information about ILUMYA™ that is written for health professionals.

What are the ingredients in ILUMYA™?

Active ingredient: tildrakizumab-asmn

Inactive ingredients: L-histidine, L-histidine hydrochloride monohydrate, polysorbate 80,

sucrose, and water for Injection, USP.

MCW Protocol No: PRO00035737 62 Version No. 7

Manufactured by: Sun Pharma Global FZE, Inc.

Sharjah, U.A.E.
U.S. License No. 2092
At: MSD Ireland (Carlow), County Carlow, Ireland
Tildrakizumab-asmn (active ingred.) Product of The Netherlands.
Distributed by: Sun Pharmaceutical Industries, Inc., Cranbury, NJ 08512
ILUMYA™ is a trademark of Sun Pharma Global FZE
Copyright © 2018 Sun Pharma Global FZE
All rights reserved
usmg-tildrakizumab-pfs-00001

This Medication Guide has been approved by the U.S. Food and Drug Administration. Issued: 08/2018

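### Section 6.1 lets tildrakizumab resume after any recovered grade 4 event with no exception for an allergic reaction to the drug, contrary to Appendix 3

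*Combined protocol and SAP*

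**What the plan says.** Section 6.1 schedules 100 mg on day -1 and on days 28, 112, 196 and 280, then lists five "contraindications for tildrakizumab dosing beyond the first dose". Item 1 is a grade 4 event under CTCAE version 5, of any kind, described as life-threatening and needing urgent treatment. It continues: "Dosing will be allowed upon recovery to grade ≤3". Items 2 to 5 are relapse or progression needing treatment, donor leukocyte infusion, grade III–IV acute GVHD, and chronic GVHD on systemic therapy. The dosing table enters None under "Premedication; precautions".

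Appendix 3, the Medication Guide, opens its serious side effects with "Serious allergic reactions. Get emergency medical help right away". It says not to use the drug "if you have had a severe allergic reaction to tildrakizumab or any of the other ingredients", and names the excipients, starting "Inactive ingredients: L-histidine, L-histidine hydrochloride monohydrate, polysorbate 80".

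Section 4.6 lists nine reasons for ending study treatment. The closest is "Unacceptable adverse event(s) beyond requirements as detailed in this protocol". Its paragraph on investigator-initiated withdrawal names the occurrence of an adverse event among the possible reasons. Section 8.6, titled Contraindications, deals only with elimination and co-administered therapies. Section 8.7 refers to the brochure or package insert for full adverse event information.

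**The concern.** Staff deciding on the next dose would look to section 6.1. For a patient who had a life-threatening allergic reaction to an earlier dose and has since recovered, that section says dosing is allowed. The opposite instruction stands in a patient leaflet at the back of the protocol, to which 6.1 makes no reference.

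At stake is re-exposure of a transplant recipient to a drug that has already caused a life-threatening reaction in that person. This is a patient-safety matter, not a threat to inference.

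**Working it through.** There is no plan figure to reproduce and no event rate in the documents. The check sets the rules side by side.

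**1. Where the rules meet.** I assume that a grade 4 allergic reaction counts as severe in the sense of Appendix 3, which gives no grade.

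| Situation | 6.1 item 1 | Appendix 3 | Conflict? |
|---|---|---|---|
| Grade 4 cytopenia or other non-allergic event, recovered | May resume | Silent | No |
| Grade 4 allergic reaction to the drug, not yet recovered | Hold | Do not use | No |
| Grade 4 allergic reaction to the drug, recovered to grade ≤3 | May resume | Do not use | **Yes** |
| Grade 3 allergic reaction to the drug | Item 1 not engaged | Do not use, if judged severe | No; 6.1 is silent |
| Severe reaction before enrolment | List starts after dose 1 | Do not use | No; exclusions are silent |

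**2. Which doses.** There are five planned doses. A reaction after dose 1, 2, 3 or 4 leaves a later dose to decide on. A first reaction after dose 5 (day 280±14) leaves none.

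**3. Does another section supply the exception?** Entries that name an allergic reaction to the drug:
- 6.1 re-dosing list: 0 of 5.
- 4.6 reasons for ending treatment: 0 of 9.
- Exclusion criteria (4.5 and Protocol Summary): 0 of 11.
- 7.6, under "Tildrakizumab side effects include": 0 of 3 (nasopharyngitis, diarrhea, injection site reaction, the last taken as local). This list does not claim to be complete.
- 8.6: no mention.

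**4. Would reporting intervene first?** Table 1 in 7.2.1 and its footnotes send a grade 4 SAE to the DSMC within 5 calendar days of staff knowledge, expected or not. If the event is unexpected and at least possibly related, it also goes to the IRB within 5 days, to FDA within 7 days when life-threatening, and to the manufacturer. Gaps between doses, using the days and windows in 6.1:
- Dose 1 to 2: 28 − (−1) = 29 days; shortest 25 − (−1) = 26.
- Dose 2 to 3: 112 − 28 = 84; shortest 105 − 31 = 74.
- Dose 3 to 4: 196 − 112 = 84; shortest 182 − 119 = 63.
- Dose 4 to 5: 280 − 196 = 84; shortest 266 − 210 = 56.

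The shortest gap, 26 days, is well over 5 days. If the reaction follows soon after the dose and is recognised promptly, the DSMC hears of it before the next planned dose. But Table 1 sets a duty to report. It does not say that the patient's next dose is withheld.

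**The case against.** The strongest reply is that the two texts can be read together. Item 1 only lifts the hold that item 1 itself imposes. The list does not claim to be exhaustive, and a specific prohibition in an appendix to the same protocol would still apply. Section 4.6 gives the investigator both a general adverse-event stop and a duty to withdraw a subject when continuing is not in that subject's interest, with an adverse event as a named reason. The DSMC is told within days and can recommend suspension. Section 8.7 points to product documents that may state the contraindication, and those are not available here. Few physicians would re-dose after anaphylaxis.

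Much of this stands, and it limits the weight of the point. It does not remove it. The reconciling reading has to be supplied by the reader, because 6.1 does not refer to Appendix 3. The 4.6 stops depend on judgment, and neither names allergy. Section 8.7 refers to the product documents for adverse event information and does not import a dosing rule from them.

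A reader might infer more than the documents support:
- *That the protocol requires re-challenge.* It does not; 6.1 permits dosing, and items 2 to 5 and section 4.6 still apply.
- *That resuming after grade 4 events is wrong in general.* For recovered cytopenias and other non-allergic events nothing in Appendix 3 conflicts.
- *That the None entry in the dosing table denies any contraindication.* It is a table entry on premedication and precautions, no more.
- *That the number of patients at risk can be stated.* No rate of severe reaction or of re-dosing is given. Counting the doses that 6.1 governs would not measure harm.

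**Conclusion.** Wrong as written: two safety rules in the same protocol conflict. The conflict is confined to a recovered grade 4 allergic reaction to tildrakizumab after one of doses 1 to 4. In that case the operative dosing section gives the unsafe answer, and no section contains a patient-level bar on the next dose other than the patient leaflet. The finding covers the protocol text only, not the brochure or package insert.

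Severity is minor. Harm needs both a rare event and a clinician's decision to re-dose despite 4.6 and Appendix 3. No probability is claimed. The 12-month GRFS endpoint, the sample size of 55 and the analyses are unaffected.

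**What to change.** Add to 6.1 item 1, and mirror in 4.6:

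> A grade 4 or otherwise severe allergic reaction to tildrakizumab or its excipients requires permanent discontinuation of tildrakizumab; the recovery to grade ≤3 allowance does not apply.

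Appendix 3 attaches no grade to severe, so any cut-off below grade 4 is for the sponsor-investigator to set. The hold-and-resume rule for non-allergic events stays as it is.

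Optional alignment with Appendix 3, beyond what the conflict itself needs: an exclusion for a known prior severe reaction to the drug or its excipients (section 4.5 and the Protocol Summary), and a matching line in 8.6.

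The cost is one sentence in two places, with no added test or visit. Under 4.6 a patient who stops treatment remains in follow-up and is not replaced. Under 10.3 the efficacy analysis set needs only one dose, so that patient still counts in the primary analysis.

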6.2 Standard GVHD Prophylaxis Administration

6.2.1 Tacrolimus

Tacrolimus will be given per standard operating procedures from the MCW BMT program, intravenously at a dose of 0.03 mg/kg/day starting day -3. Subsequent dosing will be based on blood levels. The dose should be adjusted accordingly to maintain a suggested level of 5-10 ng/mL. The dose of tacrolimus may be switched to oral at a 1:3 dose equivalence and rounded to the nearest 0.5 mg at the discretion of the treating physician. If patients are on medications which alter the metabolism of tacrolimus (e.g., azoles), the initial starting dose and subsequent doses should be altered, as per institutional practices. Tacrolimus taper can be initiated at a minimum of 90 days post-HSCT, if there is no evidence of active GVHD. The rate of tapering will be done according institutional practices, but patients should be off tacrolimus by day 180 post-HSCT.

6.2.2 Methotrexate

Methotrexate will be administered, per institutional practices, at the doses of 15 mg/m² IV bolus on day +1, and 10 mg/m² IV bolus on days +3, +6 and +11 after hematopoietic cell infusion. Dose reduction of MTX due to worsening creatinine clearance after initiation of conditioning regimen. high serum levels or development of oral mucositis is allowed, according to institutional practices.

6.3 General Concomitant Medication and Supportive Care Guidelines

There are no restricted concomitant medications.

Patients should avoid live vaccines until at least two years post-transplant as per institutional protocol.

6.4 Dietary Restrictions

There are no dietary restrictions for this study.

6.5 Supportive Care Guidelines

All supportive therapy for optimal medical care will be given during the study period at the discretion of the attending physician(s) within the parameters of the protocol and documented on source documents as concomitant medication.

Concurrent or concomitant use of medication is not restricted during protocol therapy. However, subjects are not permitted to take any anti-cancer medications or supplements during study treatment

6.6 Follow-up Period

Patients will be followed for a total 12 months or until death, whichever occurs first. All patients who receive at least one dose of the study drug will be followed.

7 ADVERSE EVENTS: DEFINITIONS AND REPORTING REQUIREMENTS

7.1 DEFINITIONS

7.1.1 Adverse Event

Any untoward medical occurrence in a patient or clinical investigation subject administered a pharmaceutical product and which does not necessarily have to have a causal relationship with this treatment. (International Conference on Harmonisation [ICH], E2A, E6). This study will utilize the NCI Common Terminology Criteria for Adverse Events (CTCAE) version 5.0, located on the CTEP web site:

https://ctep.cancer.gov/protocolDevelopment/electronic applications/ctc.htm

AEs may be spontaneously reported by the patient and/or in response to an open question from study personnel or revealed by observation, physical examination or other diagnostic procedures.

MCW Protocol No: PRO00035737 37 Version No. 7

